### III. Accounting for Pain Perception

No previous study with an NSAID has considered analgesia as a possible confounding variable in the reported augmented antidepressant response to the anti-inflammatory add-on agent. Because NSAIDs possess analgesic properties and physical pain can be variably present in depression, the issue must be considered. To underscore the point, the Sequenced Treatment Alternatives to Relieve Depression multi-center study found that 80% of 2,876 outpatients with MDD complain of painful physical symptoms (Pilowsky et al, 1984; Husain et al, 2007; Leuchter et al 2009). None of the previous studies on celecoxib excluded patients with active physical pain or sought to quantify the pain dimension during treatment. As a result, we feel it is important to control for and evaluate pain perception. Therefore, subjects with a pre-existing pain condition will not be enrolled in the study. Furthermore, we will use the Short-Form McGill Pain Inventory to assess the visit-to-visit pain perception of subjects.

## DATA ANALYSIS AND STATISTICAL METHODS

### I. Statistical Analysis

Specific Aim 1 is to determine if combined pharmacotherapy of escitalopram + celecoxib will result in earlier and/or improved affective responses compared to escitalopram + PBO. Additionally, Specific Aim 1 seeks to control for pain perception in this analysis. For this aim, the patients in the two treatment arms will be compared on HAM-D, HAM-A, MADRS, BDI, and BAI scores. This will be accomplished with an analysis of covariance conducted at weeks 1, 2, 4 and 8. Baseline mood scores and McGill Pain Inventory scores will be used as covariates. In addition, the number of patients who are and are not classified as remitters at week 8 (those having a HAM-D score of 7 or less) will be tallied and cross-referenced with treatment group (escitalopram + celecoxib or escitalopram + PBO). The frequencies in the resulting 2-by-2 contingency table will be analyzed with the Pearson Chi-Square Test for Association.

For Specific Aim 2, dealing with treatment safety and tolerability, the numbers of patients who do and do not experience adverse events at weeks 1, 2, 4, and 8 will be tallied and cross-referenced with treatment group. The frequencies in the resulting 2-by-2 contingency table will be analyzed with the Pearson Chi-Square Test for Association. Additionally, to understand whether any pharmacodynamic interaction exists between escitalopram and celecoxib, blood levels of escitalopram and celecoxib drawn at weeks 4 and 8 will be compared for patients in the two treatment groups with an analysis of covariance using baseline levels as a covariate. If there is no pharmacokinetic interaction then we expect that there will be no statistically significant results for these analyses.

For Specific Aim 3, determining whether there is a correlation between blood concentration of pro-inflammatory biomarkers and the psychiatric effectiveness of the combined treatment, three types of analyses will be conducted. First, at the end of treatment we expect that general inflammation will be lower for patients taking celecoxib. Hence, the week-8 measures of TNF-alpha and hsCRP for patients in the two treatment groups will be compared with an analysis of covariance using baseline values as a covariate. Second, based upon information from our previous research, we anticipate that patients with the highest inflammation values, who receive celecoxib with escitalopram, will derive the greatest therapeutic benefit. Hence, we expect an inflammation-by-study group interaction. Therefore, the association of Week 8 HAM-D scores and baseline TNF-alpha values will be examined by way of multiple regression analysis. Week 8 HAM-D scores will be the criterion variable. The regression equation will include predictor terms for baseline HAM-D scores (to control for pre-existing differences in mood), baseline TNF-alpha values, a dichotomous variable for study group (escitalopram+celecoxib vs. escitalopram+PBO), and the product of baseline TNF-alpha and study group. It will be the statistical significance of the last term (the product) that tests the inflammation-by-study group interaction. This analysis will be repeated with hsCRP. Third, the change in inflammation across the eight weeks of therapy will be correlated with the change in depression scores. The difference in HAM-D scores from week 8 and baseline will be correlated with the difference in TNF-alpha and then hsCRP using the Pearson Correlation Coefficient. This will be done for patients in the monotherapy group and then for those in the combination therapy group. The same analysis will be repeated using HAM-A, MADRS, BDI and BDI.

For Specific Aim 4, the effectiveness of celecoxib in inhibiting PGE2 will be analyzed by comparing PGE2 scores at week-8 for patients in the two treatment groups with an analysis of covariance using baseline PGE2 scores as a covariate. We anticipate that the adjusted mean for PGE2 at week-8 will be lower for patients receiving celecoxib than that for patients receiving PBO.

An approach for statistical analysis of Specific Aims 5, 6, and 7 is currently under development.

All statistical analyses will be conducted using the latest version of SPSS software for Windows. If a subject drops out after completing 6 weeks on active medication (after randomization), we will use the last observation carried forward (LOCF method) to analyze the data. If a subject has completed at least one week on active medication after randomization, but drops out of the study at any time between week-1 and week-8, s/he will be included in the intent-to-treat analysis. Since this project seeks to provide proof-of-concept in bipolar depression, and is therefore exploratory in nature, we propose the tests of significance use a 0.05 alpha level. However, if this proposal develops further we may adjust our desired level of statistical significance to be in line with the number of tests so that the family wise Type I error rate could be held at 5%. This issue will be considered in the future.

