### Using Celecoxib Instead of Another NSAID

There are more preliminary reports using CBX as an add-on treatment for depression than any other add-on NSAID strategy. Additionally, as a COX-2 inhibitor CBX lacks the substantive anti-platelet effects associated with other NSAIDs on the US market which are non-selective mixed COX-1/COX-2 inhibitors, such as aspirin (Riondino et al, 2008). Using CBX allows for reasonable confidence that changes (i.e., in biomarkers) could not result from indirect effects on platelets or coagulation. Furthermore, due to pharmacokinetic reasons the analgesic effects of CBX take effect slower than other NSAIDs. Having a 3-hour interval between medication ingestion and effect onset decreased the likeliness that a cue can be perceived by the patient, thereby breaking the blind.

In addition to these pharmacological issues, the use of CBX also rests on basic science findings linking COX-2 up-regulation to depression. Pro-inflammatory cytokines are known to activate the HPA axis and exert profound effects on central monoaminergic transmission (Benedovsky et al, 1991), and at least three of them (IL-1 $\beta$ , IL-6 and TNF $\alpha$ ) are acted upon by COXs. While there are multiple isoforms of COXs, the main focus of the field has been on COX-2 because it is the isoform that is cytokine-induced through NF $\kappa$ B-dependent mode (Funakoshi-Tago et al, 2008). Stressors such as depression up-regulate transcription factor NF $\kappa$ B, which is mediator of pro-inflammatory cytokines in monocytes (Miller et al, 2009). Moreover, the predominant reaction of COX-2 is conversion of arachidonic acid to prostaglandin E2 (PGE2). Increased PGE2 in saliva, serum, and CSF of depressed patients has previously been described (Lieb et al, 1983; Calabrese et al, 1986). Since PGE2 stimulates IL-6 release, it seems likely that some of the changes observed in depression with IL-6 may be related to the COX-2 pathway.

The up-regulation of PGE2 has also been described in response to different physical, psychological, or mixed trauma experimental paradigms like social crowding, immobilization, or cold restraint stress in animals.

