## **HYPOTHESES AND SPECIFIC AIMS**

**HYPOTHESIS:** The pro-inflammatory state of BPD subjects can delay, diminish or even thwart antidepressant monotherapy. Combination therapy of escitalopram + celecoxib will result in improved treatment outcomes (faster action, augmented response, and/or higher remission rates) for treatment-resistant BPD subjects. Response to antidepressant treatment in BPD subjects will be proportional to the change in pro-inflammatory status before and after treatment.

**SPECIFIC AIM #1:** Determine if combined pharmacotherapy of escitalopram + celecoxib will result in improved affective responses compared to escitalopram + placebo. Scores from the Short-Form McGill Pain Inventory will be used to control for variation in depression that could be attributed to the relief of physical pain resulting from administration of celecoxib.

**SPECIFIC AIM #2:** Determine whether combined pharmacotherapy of escitalopram + celecoxib causes any pharmacokinetic drug-drug interaction or poses safety/tolerability issues in terms of gastrointestinal bleeding or cardiovascular health. Clinical and laboratory assessments will be made throughout treatment and an adverse events inventory will be completed at each visit.

**SPECIFIC AIM #3:** Determine the blood concentration of pro-inflammatory biomarkers of all subjects before and after treatment. Determine whether there is a correlation between blood concentration of pro-inflammatory biomarkers and the psychiatric effectiveness of the combined treatment.

**SPECIFIC AIM #4:** Quantify the specific anti-inflammatory action of celecoxib by assaying for inhibition of PGE2. PGE2 concentrations will be measured from the blood of all subjects before and after treatment.

**HYPOTHESIS:** A chronic pro-inflammatory state leads to endothelial dysfunction, arterial stiffness, and dis-regulation of the autonomic nervous system with sustained sympathetic activation and diminished vagal tone.

**SPECIFIC AIM #5:** Determine whether endothelial dysfunction is present in BPD subjects and if this dysfunction will respond favorably to the combined treatment of escitalopram + celecoxib. The detection will be accomplished by means of arterial pulse wave analysis, velocity and heart rate velocity.

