## **STUDY ENDPOINTS**

The primary endpoints pertain to the main hypothesized outcome: namely, a significantly better-than-placebo mood response for escitalopram + celecoxib that is not related to altered pain perception.

The HAM-D rating scale (17 items from the 21-item scale) will be the main measure of clinical improvement. Onset of response is defined as the day of treatment when a 30% decline in the initial (day 0) HAM-D score is recorded and is maintained for two consecutive weeks. Treatment response is defined as a 50% reduction in the initial HAM-D score occurs. Symptom remission is defined as a HAM-D score of 7 or less.

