### **I. Primary Endpoint**

We seek to establish whether the combination therapy of escitalopram + celecoxib will augment antidepressant efficacy compared to escitalopram therapy alone as demonstrated by:

- a significantly earlier group response (earlier decline in HAM-D scores)
- a more robust group improvement in HAM-D scores at 8 weeks of treatment
- more patients with symptom remission than in the escitalopram + placebo group at 8 weeks

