### **III. Exclusion Criteria**

- Any abnormal findings on the physical exam, ECG, blood/urine or minor infections.
- Abnormal results on liver or bone marrow function as indicated by liver function or CBC with differential blood tests.
- Any pre-existing physical pain condition, including fibromyalgia.
- History of peptic ulcer complicated by perforation, hemorrhage, or obstruction; symptoms of peptic ulcer within 4 weeks of enrollment date.
- Substance abuse or dependence during the preceding 12 months.
- Clinically significant hypertension, anemia, liver disease, kidney disease, arthritis, diabetes, recurrent migraines, epilepsy, stroke, gum disease, autoimmune disease. Based on the judgment of the PI, a risk assessment should be done if a subject meets any of this clinical criteria but is otherwise suitable.
- Current use of lithium.
- Current use of a stimulant.
- Current use of any anticoagulant agents.
- Current use of nicotine-containing substances. Subjects who stop using nicotine-containing substances more than 1 month prior to assessment may be considered for the study.
- Certain steroids including use of hormonal birth control and any systemic or topical corticosteroids (hormone replacement therapy will be allowed).
- Unwillingness to refrain from H2 receptor antagonists, non-aspirin NSAIDs, ginko biloba, vitamin E or fish oils, or aspirin over 81 mg/day.
- Sensitivity or allergy to the study medications.
- Need to receive agents that are contraindicated in combination with celecoxib or escitalopram.
- Unwillingness to fast and abstain from caffeine on mornings of blood drawings.
- A sleep disorder other than insomnia or hypersomnia as a distinct symptom of MDD.
- Inability to commit to the follow-up visits between 8:30am and 12:00pm.

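### The Aim 1 ANCOVA does not say which visit's McGill pain score is the covariate, and neither reading gives a pain-independent mood effect without assumptions the plan leaves unstated.

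*Combined protocol and SAP*

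**What the plan says.** Under I. Statistical Analysis, Aim 1 compares the arms on five mood and anxiety scales, HAM-D among them, by a separate ANCOVA at each of weeks 1, 2, 4 and 8. The covariate sentence is "Baseline mood scores and McGill Pain Inventory scores will be used as covariates".

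Specific Aim #1 gives the purpose: McGill scores "will be used to control for variation in depression that could be attributed to the relief of physical pain resulting from administration of celecoxib". Study Endpoints describes the hoped-for mood response as one "that is not related to altered pain perception". The Primary Endpoint list is worded without that restriction, for example "a more robust group improvement in HAM-D scores at 8 weeks of treatment".

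Accounting for Pain Perception says that no earlier NSAID study "considered analgesia as a possible confounding variable in the reported augmented antidepressant response", and adds: "None of the previous studies on celecoxib excluded patients with active physical pain or sought to quantify the pain dimension during treatment". The section on choosing celecoxib refers to its analgesia directly: "the analgesic effects of CBX take effect slower than other NSAIDs". The exclusion criteria rule out "Any pre-existing physical pain condition, including fibromyalgia".

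The Schedule of Events places the McGill in the self-assessment packet at Baseline and Weeks 1, 2, 4 and 8, so a baseline or an on-treatment covariate is equally feasible.

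**The concern.** In the covariate sentence, the word for baseline may govern the mood scores alone or both scores. The two readings give different models that answer different questions. If the choice is left open, it can be made after the data are seen, on the comparison that sizes the trial.

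Pain relief that results from celecoxib is a consequence of randomised treatment. It lies on a possible path from drug to mood, so it is not a confounder in the sense the plan uses. Conditioning on it gives up the protection of randomisation. On that reading, no planned between-arm comparison of mean HAM-D is left that randomisation protects. The Aim 3 regressions omit pain but test a biomarker-by-arm interaction, and the week-8 remission chi-square, which is unaffected, uses a dichotomy.

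**Working it through.** **1. What each reading can deliver.**

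| McGill score used | Overall effect of adding celecoxib | Pain-independent effect |
|---|---|---|
| Baseline | Yes, protected by randomisation | No: it is measured before any celecoxib is taken |
| On-treatment | No | Only under assumptions |

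The stated purpose of Aim 1, the complaint that earlier studies did not quantify pain during treatment, and the endpoint wording all lean towards an on-treatment score. None names a visit, or says whether same-visit score, change or average is meant.

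**2. What on-treatment adjustment requires.** (i) Pain and mood share no unmeasured causes. (ii) Mood does not drive reported pain. (iii) There is no unmodelled treatment-by-pain interaction. (iv) Pain is measured with little error. The plan states none of them.

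**3. Direction of bias.** All parameters here are assumed, because the documents give none for pain.

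- *Shared cause.* Let on-treatment pain have within-arm variance 1, of which baseline pain explains 0.25. Let an unmeasured cause load 0.5 on both pain and mood, and let celecoxib lower pain by *a* SD. The pain slope is then inflated by (0.5 × 0.5)/(1 − 0.25) = 0.333, and the arm estimate shifts by 0.333*a* against celecoxib. With *a* = 0.5 the shift is +0.167. A true pain-independent effect of −0.45 becomes −0.283 (simulated −0.28), and a true zero becomes about +0.17 (simulated +0.16 to +0.17, rejected in 14% to 21% of 4,000 runs). With *a* = 0.8 a true zero becomes +0.267 (simulated +0.27, rejected in 29%). With *a* = 0 there is no shift.
- *Mood drives pain, no analgesia.* With both variables scaled to within-arm SD 1 and correlation *r*, an effect δ on mood produces a pain difference *r*δ. The adjusted effect is δ − *r*(*r*δ) = δ(1 − *r*²), so 9%, 16% or 25% of a real benefit is removed at *r* = 0.3, 0.4 or 0.5.
- *Measurement error.* The pain slope is attenuated, so part of any analgesic effect stays inside the supposedly pain-independent estimate, in favour of celecoxib.
- *All four assumptions hold.* With *a* = 0.5 and a pain-to-mood slope of 0.3, on-treatment adjustment recovers the pain-independent effect (true −0.45, simulated −0.45; true 0, simulated 0.00 with 5.1% rejection). The baseline-pain model returns the overall effect instead: −0.60 in the first case and −0.15 (= −0.5 × 0.3) in the second.

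**4. The plan's sample size.** Determination of Sample Size gives effect size 0.60, 45 per group, 80% power and alpha 0.05. A two-sided two-sample *t* calculation needs 44.6 per group, rounded up to 45, with power 80.4% at 45. The figure reproduces.

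That section raises published effects of 0.53 and 0.52 to about 0.60 because the ANCOVA will remove variance due to baseline levels and to pain. The 0.60 is therefore an effect *after* pain adjustment. The variance removal implied is 1 − (0.53/0.60)² = 22% to 1 − (0.52/0.60)² = 25%.

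**5. Power for the overall effect if on-treatment pain is left out.** On the plan's scale, with arms equal in pain and within-arm correlation *r* between on-treatment pain and HAM-D, the standardised effect is 0.60 × √(1 − *r*²):

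| *r* (assumed) | Effect | Power at 45 per group |
|---|---|---|
| 0.3 | 0.572 | 77% |
| 0.4 | 0.550 | 73% |
| 0.5 | 0.520 | 68% |

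At *r* = 0.5 pain alone removes 25% of variance, which is the plan's whole uplift from 0.52. Baseline McGill would recover some of the loss; how much is unknown.

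**The case against.** The strongest reply is that only a missing specification is established. The sentence can be read as baseline for both scores. The sample-size section treats pain as variance to be removed, which suits a pre-randomisation covariate. That stands: a reader might infer that the plan has committed itself to a biased analysis, and the documents do not go that far. But the baseline reading leaves the purpose stated in Aim 1 unmet, so it does not settle the matter.

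Second, the endpoint section makes the pain-independent effect a declared target. If pain simply acts on mood, a smaller adjusted effect is then the intended answer and not bias. This also stands, and it is why that analysis should be kept and its assumptions stated. The same section's list of primary endpoints, however, describes the overall augmentation effect.

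Third, patients with pain conditions are excluded and the study calls itself exploratory. If the arms barely differ in on-treatment pain, the shift is small and adjustment may gain precision. The exclusion makes a small difference plausible without ensuring it, and exploratory status does not identify the covariate.

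Two stronger readings are tempting. A reader might take 0.60 as the effect before pain adjustment and compute a large loss of power from adjusting. The sample-size section defines it as the effect after adjustment, so that calculation counts pain variance twice. A reader might also conclude that the only danger is a missed benefit. Step 3 shows that false results against celecoxib and under-adjustment in its favour are also possible.

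**Conclusion.** The point holds. The McGill visit is unspecified. A baseline score cannot support a claim of pain independence. An on-treatment score supports it only if there are no shared unmeasured causes, no effect of mood on reported pain, no unmodelled treatment-by-pain interaction and little measurement error, and it does not estimate the overall effect.

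The size and net direction of any bias cannot be derived from the documents, which give neither the arm difference in on-treatment pain nor the pain-mood correlation. The simulated values show direction and possibility only. The 45 per group is correct for its stated inputs and is not in dispute. This should be fixed before analysis. Confidence is medium, because which reading was intended is not settled.

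**What to change.** In I. Statistical Analysis:

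1. State the McGill visit.
2. Adjust the Aim 1 ANCOVA of each scale for that scale's baseline score and baseline McGill, as the randomisation-protected estimate of overall effect.
3. Compare McGill scores between arms at weeks 1, 2, 4 and 8.
4. Prespecify alongside it an on-treatment-pain-adjusted or mediation analysis for the pain-independence question, with all four assumptions stated and a sensitivity analysis.
5. Make the pain-independence claim only from both analyses together.

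**Cost.** The McGill is already collected at every visit needed. The change goes beyond wording: the overall effect gets its own estimate, and the pain-independence claim comes to depend openly on assumptions. On-treatment pain no longer reduces variance in the overall-effect model, so power there may fall below 80% by the amounts in step 5, less what baseline McGill recovers. Determination of Sample Size should say so.

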At the Baseline visit, subjects will be reassessed for depression and associated symptoms. If subjects continue to score 18 or higher on the 17-item HAM-D scale, they will be randomized to receive escitalopram + celecoxib, or escitalopram + placebo in an assignment ratio 1:1. Subjects will then go on to complete assessments at Week 1, Week 2, Week 4 and Week 8. If the subject scores below 18 on the 17-item HAM-D scale at Baseline, he or she will be terminated from the study and classified as a placebo responder. At each of these visits, subjects will arrive 30 minutes before their scheduled appointment time, rest for 20 minutes in the exam room, and provide a saliva sample prior to undergoing any assessments. Terminated subjects will be offered conventional care at the same institution.

It is our desire to observe the diurnal nature of cortisol levels in saliva by measuring the patient's salivary cortisol levels at a time point prior to treatment and post treatment. At each of these two time points, we would collect saliva from the patient at five times during the day: upon awakening, approximately 30 minutes past awakening, before lunch, at approximately 3pm, and before bedtime. The patient would be required to do this at home and would then store the samples in their refrigerator until their next visit. Subjects will be provided with a log to record the exact time of saliva collection. We will be using salivettes purchased from Sarstedt Inc., and our Salivary Assay kits will be purchased from Salimetrics, LLC.

The overall study is powered for 90 subjects. We aim to randomize 70 subjects at LUMC. Approximately 30 subjects will be randomized by investigators at our sister site in Munich, Germany. At LUMC, 35 subjects will be randomized to each arm of the study. Subjects must complete 8 weeks of active medication to be considered study completers. We plan to enroll approximately 80 patients in anticipation of a 10% drop-out rate. The drop-out rate is based on our experience with our patient population over the past 5 years. If a subject drops out or is terminated after Week 6, their last observation will be carried forward in the analysis (LOCF). There are no healthy controls in this study because we already possess normative, untreated data for comparison.

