## II. Determination of Sample Size

Although a number of tests of statistical significance are planned for the proposed study, our required sample size is being based upon the primary outcome of treatment effect (Specific Aims 1). In looking at differences in mean HAM-D scores from the studies by Akhondzadeh et al. 5 and Mueller et al. 6 we found that the effect sizes of an antidepressant + anti-inflammatory agent over an antidepressant + placebo at week 3 of treatment were 0.53 and 0.52, respectively. In the proposed research we anticipate that the effect size will be slightly higher due to the fact that variation in depression scores attributable to baseline levels and pain perception will be eliminated in an analysis of covariance. Hence, we anticipate that the effect size will be about 0.60 for escitalopram + celecoxib over escitalopram + PBO. As noted earlier, we anticipate that the drug combination will lead to a therapeutic response that is earlier than what is normally seen at week-3 of treatment. We thus expect to see a treatment effect at week-2 of therapy, and expect that the magnitude of the effect will increase over the course of the study. The increasing separation between the different treatment groups is similar to what was found in the studies mentioned above which observed rising treatment effects during the course of therapy. From this, our computations indicate that a sample size of 45 patients per group will provide 80% power for an analysis of covariance to detect an effect size of 0.60 at week-2 of therapy using a 0.05 level of significance. Thus, a total of 90 patients completing treatment will be acquired for the proposed work. 30 of the total patients will be enrolled and randomized at our sister site in Munich, Germany. Given that the therapeutic effect size is expected to increase over time, the proposed sample size will be adequate throughout the course of the study. Subjects lost to attrition will be replaced.

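### Week-8 remission, one of three primary results, is tested without baseline HAM-D: the test is valid, but a small and cheap gain in power is left unused

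*Combined protocol and SAP*

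**What the plan says.** The Primary Endpoint section lists three results. The third is "more patients with symptom remission than in the escitalopram + placebo group at 8 weeks". Remission means a HAM-D of 7 or less.

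Under Specific Aim 1, the Statistical Analysis section gives remission a single test: "The frequencies in the resulting 2-by-2 contingency table will be analyzed with the Pearson Chi-Square Test for Association". (The same sentence is used for adverse events under Aim 2, which is not at issue here.) For the scale scores, the same Aim 1 paragraph plans an ANCOVA: "Baseline mood scores and McGill Pain Inventory scores will be used as covariates".

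The sample size section starts from published effect sizes that "at week 3 of treatment were 0.53 and 0.52, respectively" and raises them to about 0.60 because "variation in depression scores attributable to baseline levels and pain perception will be eliminated in an analysis of covariance".

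There are two sites. The sample size section says "30 of the total patients will be enrolled and randomized at our sister site in Munich, Germany", and Study Design gives a similar figure. No Aim 1 analysis includes site, and stratified randomisation is not mentioned. The site totals do not agree: 70 at LUMC plus about 30 in Munich is 100, against a powered total of 90.

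**The concern.** Remission is week-8 HAM-D cut at 7. The plan counts on baseline HAM-D, together with pain, to remove outcome variance in the ANCOVA, but drops baseline when the same scale is dichotomised. If baseline predicts week-8 HAM-D, the chi-square gives up some power on a primary result in a small trial, and the plan states no power for that result. Site is a lesser matter: it costs power only if outcomes differ between LUMC and Munich.

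**Working it through.** **1. The plan's own figure.** For an effect of 0.60, 80% power and two-sided 0.05 (sidedness is not stated; one-sided would give 35), n = 2(1.96 + 0.84)²/0.60² ≈ 43.6, so 44 per group. The t-based solution is 44.6, so 45, with power 0.804. The stated 45 per group is reproduced. It applies to the week-2 HAM-D ANCOVA. There is no remission figure to reproduce.

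**2. Inputs.**
- Effect: 0.525 SD, the mean of 0.53 and 0.52 (sample size section).
- Arms: 45 (30 LUMC + 15 Munich, from the total of 90) or 50 (35 LUMC per arm from Study Design + 15 Munich). An equal arm split in Munich is assumed.
- Baseline HAM-D truncated at 18 (Study Design); mean 22 and SD 4 before truncation are assumed.
- Control remission 10%, 20%, 30% or 40%: assumed.
- Correlation r of baseline with week-8 HAM-D: 0, 0.3 or 0.48, assumed. The last follows from the plan's rise to 0.60: r² = 1 − (0.525/0.60)² = 0.234, r = 0.48. It is an upper end, because it credits baseline alone with what the plan attributes to baseline and pain together.

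On a normal scale, p₁ = Φ(Φ⁻¹(p₀) + 0.525) turns 10, 20, 30 and 40% into 22.5, 37.6, 50.0 and 60.7%.

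**3. Simulated power (%), no site difference.** Each cell is chi-square → logistic score test for arm, adjusted for baseline HAM-D and site. There were 20,000 replicates per setting (10,000 in the last row).

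| Per arm | r | 10% | 20% | 30% | 40% |
|---|---|---|---|---|---|
| 45 | 0 | 38.3 → 37.5 | 47.2 → 46.7 | 48.9 → 50.0 | 48.9 → 50.6 |
| 45 | 0.3 | 38.3 → 38.6 | 46.6 → 47.9 | 49.0 → 52.6 | 49.3 → 53.8 |
| 45 | 0.48 | 39.1 → 41.8 | 48.2 → 52.6 | 49.5 → 57.0 | 49.1 → 57.5 |
| 50 | 0 | 41.2 → 40.4 | 50.3 → 50.9 | 54.1 → 54.1 | 57.2 → 56.0 |
| 50 | 0.3 | 41.8 → 42.5 | 49.8 → 52.3 | 55.3 → 57.2 | 57.4 → 58.2 |
| 50 | 0.48 | 43.3 → 46.0 | not shown | 55.2 → 61.6 | not shown |

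Over all four rates, the gain at 50 per arm and r = 0.48 is about 2 to 7 points. Part of the gain at 45 per arm comes from the discreteness of the chi-square. At 40% and r = 0 its power moves from 48.9 to 57.2 when five patients per arm are added, and the score test gains 1.7 points at 45 although the covariates carry no information.

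**4. Level.** Over r of 0 to 0.48, remission of 10 to 40% and site differences of 0 to 1.0 SD, type I error was 3.5–6.0% for the chi-square, 5.1–5.8% for the score test and 2.2–5.3% for the Wald test. Multiplying the score statistic by (N − 3)/N brings it to 4.8–5.2%. In a separate run at 45 per arm, the change in power against the chi-square after scaling (10/20/30/40%) was:
- r = 0: −2.2, −1.4, −0.4, +0.6
- r = 0.3: −0.6, +0.5, +2.2, +3.5
- r = 0.48: +1.4, +3.1, +5.8, +7.8

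At 50 per arm and r = 0.3 it was −0.5, +1.3, +0.8, −0.5. The Wald test is a poor substitute: at 45 per arm and 10% remission its power is 32.6, 33.6 and 37.3 for the three values of r, against 38.3, 38.3 and 39.1 for the chi-square.

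**5. Site.** Without a site difference, site adds about 0.5 point or less to the score test. HAM-D ANCOVA power without and with site (45 per arm, r = 0.3) is 73.4 and 73.4 with no difference, and 70.5 and 72.5 with an assumed 0.5 SD difference.

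**6. Larger effect at week 8.** At 45 per arm, 30% remission and r = 0.3, effects of 0.60, 0.70 and 0.80 give 60.5 → 64.5, 73.9 → 77.4 and 83.8 → 87.4.

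**The case against.** An unadjusted chi-square on a randomised binary outcome is a legitimate choice. The plan calls the trial proof-of-concept and exploratory, sizes it on the HAM-D ANCOVA, and already has a baseline-adjusted week-8 HAM-D comparison. At the 35 LUMC patients per arm that Study Design states, the gain at r = 0.3 is small and almost vanishes after scaling. Any gain above about 5 points needs r = 0.48 or an assumed site difference, and the documents give neither a week-8 correlation nor a site difference.

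All of that stands, and it limits the point to a modest suggestion. It does not remove it: baseline HAM-D is already collected, the plan itself treats it as prognostic, and the change is one of wording.

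Four stronger readings are tempting and are not supported:
- That the chi-square is wrong. It is valid.
- That remission has only about 50% power. That holds only if the week-3 effect still applies at week 8, whereas the authors "expect that the magnitude of the effect will increase over the course of the study".
- That leaving out site is a demonstrated loss. With no site difference there is nothing material to gain.
- That adding the McGill score would separate mood from pain relief in the remission test. A baseline pain score cannot account for pain that treatment changes.

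**Conclusion.** The point holds as a small efficiency improvement. The remission test ignores a covariate that the plan uses, and relies on, for the same scale. Before scaling, the likely benefit is between nothing and about 5 points of power at a moderate baseline correlation, at the lower end of that range if 50 per arm are randomised, and up to about 8 points at the upper-end correlation. If the covariates are not prognostic, about 1 point is lost, or about 2 with scaling. That loss is not confined to low remission rates: it also appears at 40% with 50 per arm. Every figure rests on assumed remission rates, correlations and arm split. Site is secondary, worth about 2 points in the ANCOVA if the sites differ by 0.5 SD.

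**What to change.** - Make the primary remission test a logistic score test for arm, adjusted for baseline HAM-D, with the statistic multiplied by (N − 3)/N. Do not use the Wald p-value. Keep the chi-square as a sensitivity check.
- Take significance from the score test only. If a standardised risk difference is reported, either state that its delta-method interval is slightly too narrow at this sample size (type I error 5.6–6.5% in simulation) or use an interval with a small-sample correction.
- Secondarily, add site (LUMC or Munich) as a fixed factor to the remission test and to the HAM-D ANCOVA. This costs one degree of freedom.
- The Statistical Analysis section fixes SPSS, so confirm that the version used reports the score statistic for arm.

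The change is SAP wording on data already collected. It needs no extra patients or visits and leaves the analyses for Aims 2 to 4 as they are. The price is the small possible loss of power given in the verdict.
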